This is a multi-institution, prospective, randomized study evaluating IVFE dose reduction on the development of PNAC as a proxy measure of PNALD in neonates requiring prolonged PN. The definition of PNAC will be that used predominantly in the literature – a direct bilirubin level of ≥ 2 mg/dL, documented on two occasions 1 week apart, in patients who have required parenteral nutrition for more than 2 weeks. **Eligible neonates will be randomized into two treatment arms: standard IVFE administration (3 g/kg/day) or IVFE reduction (IFER) (1 g/kg/day).** A total of 60 subjects (30 subjects per arm) will be included in the study. The study will evaluate

short- and long-term outcomes of this strategy. In the short-term, infants will be followed for up to 12 weeks for the development of PNAC. If a subject's PN is discontinued before 12 weeks, and if they remain in the hospital, follow-up data will be collected for an additional 7 days but not beyond a total of 84 days. Only standard-of-care data will be collected during these 7 days. No procedures will be performed for the purpose of this study during these 7 days. In the long-term, subjects' neurodevelopmental outcomes will be assessed at 12 and 24 months corrected gestational age (± 2 weeks).

Primary outcome measure:

1. The rate of rise of direct bilirubin as a function of time (mg/dL/week) between the two groups over 12 weeks or until the subject has been off of PN for >7 days, whichever comes first.

Secondary outcome measures

1. Initial 12 week period:
 - a. The incidence of PNAC (direct bilirubin ≥ 2 mg/dL) and severe PNAC (direct bilirubin ≥ 4 mg/dL in subjects on parenteral nutrition for at least 2 weeks)
 - b. The time to development of PNAC and severe PNAC
 - c. The peak total and direct bilirubin levels
 - d. The incidence of EFAD
 - e. Adequacy of growth as evaluated by z-scores for weight, height, and head circumference
 - f. Other safety measures assessed during the initial 12 week period will include adverse events (e.g., episodes of sepsis and catheter-related blood stream infections).
2. Long-term follow-up:

Neurodevelopmental assessments will include:

 - a. At 12 months corrected gestational age (± 2 weeks):
 - i. Bayley Scales for Infant and Toddler Development (BSID-III)
 - b. At 24 months corrected gestational age (± 2 weeks):
 - i. Bayley Scales for Infant and Toddler Development (BSID-III)
 - ii. MacArthur-Bates Communicative Development Inventories (CDI)

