14. Hypoxic ischemic encephalopathy

Standard IV lipid dosing compared to IV lipid minimization for the prevention of PNAC/PNALD

15. Congenital defect of the brain
16. Major seizure disorder

Removal from Study Protocol After Initiation of Study

The following criteria may require study removal:

1. Parent or guardian request for removal
2. Transfer to a non-study hospital
3. Development of multiple nutritional problems which are unable to be managed (e.g. more than mild undernutrition, irreversible undernutrition, hyperglycemia, or hypertriglyceridemia refractory to intervention)
4. At the discretion of the PI

Informed Consent

Informed consent will be obtained from the parents or legal guardian of the child. Consent will be obtained in person whenever possible. In the rare circumstance that a parent or legal guardian cannot be present in person, consent will be obtained via telephone. We expect this to be an unusual occurrence as subjects can be randomized up to 72 hours after PN initiation.

Randomization

Subjects will be randomized within 72 hours of PN initiation. Stratified, equal within-center randomization will be performed after consent is obtained. Group assignment will be determined by a random permutation of blocks of randomly determined sizes of 2 or 4. Randomization will be stratified based on gestational age (<32 and ≥32 weeks gestation). Enrollment and randomization will occur as early as feasible after identification of subjects who meet eligibility criteria. Randomization MUST occur within 72 hours of PN initiation to minimize the number of days of PN prior to treatment group assignment. All subjects will be treated according to standard management until consent is obtained and randomization occurs. Once randomization occurs the PN dose the subject is currently on may change based on group assignment.

Blinding

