The MacArthur-Bates Communicative Development Inventories (CDI):⁴⁶ The MacArthur-Bates CDI is the most widely used parent report measure of language development. The CDI includes two versions: Words and Gestures for ages 8-16 months and Words and Sentences for children ages 16-30 months. Scores are reported as percentiles compared to age-standardized norms.

Brief Infant Toddler Social Emotional Assessment (BITSEA):^{43,44,47} The 42-item BITSEA is a parent report measure of social-emotional and behavior problems in children ages 1-3. The Problem Index includes internalizing, externalizing and dysregulation problems. The internalizing scale has items that assess depression, anxiety and negative emotionality.

Gross Motor Function Classification System (GMFCS):^{48,49} The GMFCS is a five level classification system that assess the gross motor function of children with and at risk for cerebral palsy, from infancy through age 12. It differentiates children into one of five levels of functioning, based on the child's current gross motor ability, limitations in function, and need for assistive technology.

Behavior Assessment System for Children – Second Edition Preschool, Parent (BASC-2 Preschool Parent's version):⁵⁰ The BASC-2 PRS-P is a 134 item questionnaire that assesses psychological status and adaptive behavior. The parent/caregiver rates the occurrence of behaviors using a 4-point rating scale. The profile yields eight clinical scales (hyperactivity, aggression, anxiety, depression, somatization, atypicality, withdrawal and attention problems) and four adaptive scales (adaptability, social skills, activities of daily living and functional communication) as well as four composite scores (externalizing problems, internalizing problems, adaptive skills and the Behavioral Symptoms Index).

These neurodevelopmental tools will be evaluated on the following schedule:

12 month follow-up	24 month follow-up
--------------------	--------------------

BSID-III	BSID-III, CDI, BITSEA, GMFS, BASC-2
----------	-------------------------------------

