The MacArthur-Bates Communicative Development Inventories (CDI):⁴⁶ The MacArthur-Bates CDI is the most widely used parent report measure of language development. The CDI includes two versions: Words and Gestures (ages 8-16 months) and Words and Sentences (ages 16-30 months). Scores are reported as percentiles compared to age-standardized norms.

Brief Infant Toddler Social Emotional Assessment (BITSEA):^{44,47,55} Dichotomous scores are generated based on cut-off scores, which identify subjects to be at risk. Internal consistency coefficients range from .80 to .82. Test-retest reliability is acceptable at .80-.85. Recent evidence identifies the BITSEA as the best short tool for early detection of psychosocial problems in two-year olds.⁴⁰

Gross Motor Function Classification System (GMFCS):^{48,56} Interrater reliability is 0.75 and both content and predictive validity are well-demonstrated in child and adult populations.⁵⁶⁻⁵⁸

Behavior Assessment System for Children – Second Edition Preschool, Parent Preschool Parent’s version (BASC-2 PRS-P):⁵⁰ Limited construct validation data indicate strong correlations with similar scale scores. Primary measurements from the BASC-2 including the Adaptive Behavior Composite and the Behavior Symptoms Index will be reported as T-scores and as percentiles. Secondary analyses will be conducted on the subscales.

For the comparison of the two treatment arms across time for neurological measures that are approximately continuous, a linear mixed model will be used with a repeated measures covariance structure. The best covariance structure will be chosen based on a comparison of the Akaike Information Criterion (AIC) and Bayes Information Criterion (BIC). This will allow us to adjust for correlated measures within a subject and possibly for unequal variances across times points and across groups. Each measure will be compared between the groups at each time point, controlling for important demographic variables, such as gestational age, diagnosis, bilirubin (total and direct), as well as a time-varying covariate for development of essential fatty acid deficiency. Importantly, we will also evaluate the influence of three IFER-related variables on neurodevelopmental

Standard IV lipid dosing compared to IV lipid minimization for the prevention of PNAC/PNALD

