outcomes: mean IVFE dose, duration of IFER and the development of essential fatty acid deficiency. Since total and direct bilirubin are expected to be highly collinear, we will use only one of these predictors and compare the models using AIC and BIC to decide which is a better predictor of the particular outcome being assessed.

A logistic regression with Generalized Estimating Equations (GEE) approach will be used to compare the binary outcomes between groups.

Intent to Treat

All statistical analyses will be performed using an intent to treat approach.

Potential Confounding Variables:

Nutritional intake: Differences in nutritional intake alter the risk of PNAC as any amount of enteral nutrition has been shown to enhance rehabilitation.⁵⁹ Infants able to tolerate even trophic amounts of enteral calories will be at decreased risk compared to those than those who are completely PN-dependent. Every attempt will be made to standardize enteral feeding advancement. This will be possible because of the relatively homogeneous nature of the subjects enrolled and their similar expected ability to tolerate enteral feeds. Statistical analyses will account for variations in enteral intake. Overfeeding may result in hepatic steatosis that can also worsen PNAC, therefore all subjects will follow a strict guideline for PN administration. Additionally, the administration of breast milk, which contains proteins necessary for optimal brain development, may be a confounding variable and will be accounted for in the final data analysis. PN duration (with or without IFER) may also affect neurodevelopmental outcomes and will be included as a covariate in the statistical analysis.

Variation in IVFE dose: The IVFE dose may vary depending on the clinical status of the subject (e.g. elevated TG, EFAD, direct bilirubin ≥ 2.5 mg/dL, nutritional and/or fluid status). Every attempt will be made to maintain dosing within the assigned treatment arm. Based on previous experience using IFER at the University of Michigan, hypertriglyceridemia and EFAD are exceedingly rare occurrences, therefore, the IVFE dose is not expected to be adjusted frequently based on these findings. Statistical analysis will account for differences in IVFE dose by using the mean IVFE dose as well as the duration of IVFE/IFER as a covariate.

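### The only stated scoring of the 24-month BITSEA is at-risk yes/no; comparing the arms on the full score would use the same data more precisely (low-severity improvement to one secondary outcome)

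*Combined protocol and SAP*

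**What the plan says.** The section Neurodevelopmental Outcome Measures introduces the instrument: "The 42-item BITSEA is a parent report measure of social-emotional and behavior problems in children ages 1-3". It mentions a Problem Index, so a graded score lies beneath any cut-off. The schedule in that section lists the BITSEA only at the 24-month visit ("BSID-III, CDI, BITSEA, GMFS, BASC-2"); the 12-month visit has the BSID-III alone.

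Under Planned Statistical Analysis, Secondary Outcome Measures, item 5, the BITSEA entry gives one scoring rule: "Dichotomous scores are generated based on cut-off scores, which identify subjects to be at risk". The same item ends with two model statements. The first is for "neurological measures that are approximately continuous, a linear mixed model will be used with a repeated measures covariance structure". The second reads: "A logistic regression with Generalized Estimating Equations (GEE) approach will be used to compare the binary outcomes between groups". Neither names the BITSEA.

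The other instruments are described differently: composite and subscale scores for the BSID-III, percentiles for the CDI, five levels for the GMFCS. The main BASC-2 measures "will be reported as T-scores and as percentiles".

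On size, Study Design states: "A total of 60 subjects (30 subjects per arm) will be included in the study". Sample Size Determination gives no calculation for the BITSEA and says that the secondary outcomes other than cholestasis can show trends only. Secondary Hypothesis 3 expects neurodevelopment to be alike in the two arms and gives no margin.

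**The concern.** A cut-off answers a screening question: should this child be referred? The trial asks whether the two arms differ on average, and the plan gives no reason for using the cut there. An infant just over the threshold then counts the same as one far above it, and shifts that do not cross the threshold are invisible. The graded score has to be derived anyway before the cut can be applied.

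The stake is precision in a small trial. The plan hopes to find the arms alike, so a noisier comparison leans towards the hoped-for reading: a non-significant odds ratio could be taken as reassurance when its interval is very wide.

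**Working it through.** **Inputs from the documents.** 30 per arm (Study Design), equal allocation ("Stratified, equal within-center randomization will be performed after consent is obtained", Randomization), significance level 0.05 (Sample Size Determination), one BITSEA measurement.

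**Assumptions, not in the documents.** Two-sided test; normal scores with equal SD; standard-arm at-risk share p of 15%, 25% or 35%; IFER-arm mean shifted towards more problems by d = 0.2, 0.5 or 0.8 SD; no covariates; all 30 per arm tested at 24 months.

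**The plan's own binary figure.** There is none for the BITSEA. The one binary outcome that the plan sizes is cholestasis, 50% against 10%, 80% power, 23 per group. Fisher's exact test gives 78.6% power at 22 per group and 81.1% at 23, so 23 is reproduced.

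**Step 1: information kept by the cut.** For a small shift in a normal score, efficiency relative to the full score is φ(z)²/[p(1−p)], where z is the cut-off in SD units.

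| p | z | φ(z) | Efficiency | Information lost |
|---|---|---|---|---|
| 15% | 1.036 | 0.2332 | 0.0544/0.1275 = 0.43 | 57% |
| 25% | 0.674 | 0.3178 | 0.1010/0.1875 = 0.54 | 46% |
| 35% | 0.385 | 0.3704 | 0.1372/0.2275 = 0.60 | 40% |

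Thirty infants per arm then carry the information of about 30 × 0.43 = 13 to 30 × 0.60 = 18. Widening p to 10-50% gives a loss of 36-66%.

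**Step 2: skewed scores.** Take gamma scores with shape 3 and a difference in scale. The cut's efficacy is [c·f(c)]²/[p(1−p)] = 1.719, 1.904 and 1.913 for the three shares. That of the Wilcoxon test is 12[∫x f(x)² dx]² = 2.637. The ratios are 0.65, 0.72 and 0.73, a loss of 27-35%. Against a comparison of means (efficacy 3) the ratios are 0.57, 0.63 and 0.64, a loss of 36-43%. At each share the loss is smaller than with normal scores.

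**Step 3: power at 30 per arm, p = 25%.** With one time point and arm only, logistic GEE is in effect a logistic Wald test. The IFER-arm share is 1 − Φ(0.674 − d). Binary power comes from enumerating all 2×2 tables, and score power from the noncentral t distribution.

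| Shift d | IFER-arm share | Score (t-test) | Logistic Wald | Chi-square |
|---|---|---|---|---|
| 0.2 SD | 31.8% | 12% | 7.5% | 9% |
| 0.5 SD | 43.1% | 48% | 29% | 31% |
| 0.8 SD | 55.0% | 86% | 67% | 67% |

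Over p = 15-35%, the gain over the Wald test is about 3-7 points at 0.2 SD, 14-25 at 0.5 SD and 17-29 at 0.8 SD.

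**Step 4: precision if the arms are equal, n = 30, p = 25%.**
- SE of the log odds ratio: √[2/(30 × 0.25 × 0.75)] = 0.596.
- Half-width: 1.96 × 0.596 = 1.169, so the odds ratio interval runs from 1/3.2 to 3.2.
- In score units: 1.169 × 0.1875/0.3178 = 0.69 SD.
- From the score itself: 1.96 × √(2/30) = 0.51 SD.

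**The case against.** Several points on the other side stand.

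- **The cut as sole analysis is inferred.** The scoring sentence sits in an instrument description beside reliability coefficients. Nothing says that the score will be discarded, and the sentence on continuous measures does not exclude the BITSEA. A reader might infer that the plan rules out a full-score analysis; the documents do not support that. They state the cut and leave the rest unsaid.
- **The behaviour domain already has a full-scale measure.** The BASC-2 is given at the same visit, reported as T-scores, with subscale analyses. The at-risk proportion is a readable complement. This lowers the severity.
- **Most of the weakness is not due to the cut.** Power on the full score is still only 48% at 0.5 SD, and the plan claims no more than trends for this outcome. A reader might infer that the cut is what prevents a conclusion of similarity. It is not: no margin is stated, and ±0.51 SD would not settle the matter either.
- **The 33% attrition figure does not apply.** It is tempting to work with 20 per arm at 24 months. That allowance concerns infants leaving PN before 12 weeks, and they remain on study until 24 months. The documents give no 24-month retention.
- **GEE is not an error here.** With one measurement it estimates the same odds ratio as ordinary logistic regression.

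What the objection does not remove is that the plan states one scoring rule, the cut, and no analysis of a score that must be collected anyway.

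**Conclusion.** The point holds as a low-severity improvement to one unpowered secondary outcome. As written, the BITSEA most naturally falls to a binary comparison, which is an inefficient way to compare arms in at most 60 infants. The 40-57% loss requires normal scores and 15-35% at risk; neither is in the documents, so the range should not be quoted as a property of this trial. The power gain is about 19 points at 0.5 and 0.8 SD with 30 per arm and 25% at risk, and about 4 points at 0.2 SD. Fewer infants tested at 24 months would lower power under either analysis. The dependable benefit is a narrower interval, by roughly a quarter in the worked case (0.51/0.69 = 0.74).

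**What to change.** In the BITSEA entry of item 5, state that the between-arm comparison at 24 months uses the full score: the Problem score, and any other BITSEA score to which a cut-off is applied. Specify in advance:

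- a linear model with arm and the two baseline factors already listed for these outcomes, gestational age and diagnosis, reported as a mean difference with a 95% confidence interval;
- one rank-based sensitivity analysis, such as a Wilcoxon test with a Hodges-Lehmann interval, reported whatever the score distribution looks like, so that the data do not choose the method;
- the at-risk proportion in each arm as a descriptive result with an exact confidence interval.

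Because the BITSEA is measured once, ordinary regression can replace GEE for it. This is a simplification and does not correct an error.

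The cost is wording only, with no new data or visits. The downside is that a mean score difference is harder to read than a percentage at risk, which is why the percentage stays. The change does not supply a similarity margin; that would need its own statement.

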Standard IV lipid dosing compared to IV lipid minimization for the prevention of PNAC/PNALD

Clinical Protocol

Study Title: Standard IV lipid dosing compared to IV lipid minimization for the prevention of PNAC/PNALD (HUM00075458)

Sponsor Investigator: [name]

IND: 121287

Version 22 JUN 2018

NCT02357576

Study Significance/Background

Parenteral nutrition (PN) is the intravenous administration of complete and balanced nutrition; it has transformed nutritional support for patients who cannot maintain adequate nutrition via the gastrointestinal tract.¹ PN is associated with a number of significant infectious and metabolic complications including parenteral nutrition-associated cholestasis (PNAC) which can lead to parenteral nutrition-associated liver disease (PNALD). Both are considered among the most challenging complications associated with prolonged PN administration. PNAC is generally accepted to occur when the direct bilirubin rises above 2 mg/dL after other potential etiologies of direct hyperbilirubinemia have been eliminated.²⁻⁵ The reported incidence of liver dysfunction in children on long term PN in the literature ranges from 7.4% to 84%; this variety is attributed to study heterogeneity – the patient population studied, the definition of liver dysfunction used and different risk factors associated with the development of liver disease itself.^{6,7}

Well-characterized risk factors for the development of PNAC include prematurity, low birth weight, repeated infectious/septic episodes, a lack of enteral feeds, delayed initiation of enteral feeds and the length of time on PN.⁸⁻¹⁰ Progressive PNAC may lead to PNALD as demonstrated by severe liver injury and fibrosis which can ultimately lead to death from liver failure if transplantation is not achieved. The development of PNALD itself is associated with increased morbidity and mortality related to recurrent line infections, sepsis, the need for repeated hospitalizations and operative procedures, biliary sludge and gallstones, bacterial overgrowth and translocation.^{6,9,11} In a study of surgical neonates, almost one-third died with long-standing PNALD.¹² In a more recent study of children with short bowel syndrome maintained on long term PN, PNALD was the greatest risk factor for mortality.¹³

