 - iii. Brief Infant Toddler Social Emotional Assessment (BITSEA)
 - iv. Gross Motor Function Classification System (GMFCS)
 - v. Behavioral Assessment System for Children-Second Edition (BASC2)

Study Arms:

[figure not shown]
Study Arm 1 (Standard IVFE dosing): Subjects in the standard IVFE dosing arm (3 g/kg/day) will be on treatment for a total of 12 weeks or until the subject has been off of parenteral nutrition for >7 days, or if they are discharged from the hospital, whichever comes first.

Study Arm 2 (IFER dosing): Subjects in the IFER dosing arm (1 g/kg/day) will be on treatment for a total of 12 weeks or until the subject has been off parenteral nutrition for >7 days, or if they are discharged from the hospital, whichever comes first.

All subjects will be maintained at their assigned dosing regimen for the duration of the treatment period (12 weeks) or until they are transitioned off of PN for >7 days, are discharged or until the direct bilirubin is ≥ 2.5 mg/dL for 2 consecutive weeks, whichever occurs first. Data will be collected for the duration of the study for those subjects who remain on parenteral nutrition for the full 12 weeks. For those who transition off of PN prior to the end of the 12 week period, data will be collected for 7 days after termination of PN if the subject remains in the hospital. The clinical course of these subjects who wean off PN prior to 12 weeks will continue to be monitored according to standards of practice. If serum direct bilirubin reaches a level of ≥ 2.5 mg/dL for 2 consecutive weeks during the course of the treatment, subjects will be transitioned to an IVFE dose of 1 g/kg/day three days per week. Those who remain cholestatic at the termination of their treatment period will be evaluated on a monthly basis for the persistence or resolution of cholestasis. This will be done by obtaining monthly liver function tests and bilirubin fractions for 6 months.

Overview of Study Design:

Study Design

Inclusion Criteria

Study subjects will be neonates and infants who are ≥ 28 weeks corrected gestational age at the time of enrollment who are parenteral nutrition naïve (<72 hours of PN exposure prior to randomization) and whose direct bilirubin has never been >2 mg/dL with at least one of the following diagnoses:

1. Meconium ileus and peritonitis
2. Gastroschisis
3. Omphalocele >4 cm in diameter or with liver herniated outside of the abdominal cavity

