4. Necrotizing enterocolitis requiring surgical intervention (drain placement, laparotomy, bowel resection)
5. Volvulus
6. Intestinal atresia with >50% bowel loss as defined by bowel length nomogram (**Figure 1**)

[figure not shown]

Figure 1. Nomogram estimating normal small bowel length based on height at the time of surgery.²⁶

This population was selected because of their high risk for developing PNAC due to their underlying disease process and limited ability to tolerate enteral feeds. Using this group of subjects will allow for sufficient data to be obtained with the fewest number of subjects over the shortest period of time.

No preference will be given to sex, race or ethnic background during the enrollment of subjects into the study.

Exclusion Criteria

1. Birthweight <1kg
2. A metabolic pathway defect which is associated with liver dysfunction in the neonatal period including: hereditary fructose intolerance, galactosemia due to transferase deficiency and neonatal tyrosinemia, and/or disorders of lipid metabolism
3. A history of hepatic insufficiency as defined by either a biopsy with cirrhosis and/or a marked aberration in synthetic function (defined by elevated prothrombin time (INR ≥ 2.0) with no evidence of a systemic coagulopathy and no administration of an anticoagulant)
4. Primary or secondary liver disease, including hepatitis, as defined by either an elevated prothrombin time (INR ≥ 2.0) or elevation of liver function tests (AST and ALT) greater than twice the upper limit of the age-adjusted norm
5. Congenital obstruction of the hepatobiliary tree (e.g. biliary atresia, choledochal cyst)
6. History of PNAC or a direct bilirubin >2 mg/dL at any time prior to enrollment/randomization
7. Renal failure (as defined by a creatinine >1.5 mg/dL)
8. Use of extracorporeal membrane oxygenation (ECMO), as hemolysis from the ECMO circuit may cause a mixed hyperbilirubinemia unrelated to the development of PNAC
9. Documented active infection which may be communicable, including infectious hepatitis or human immunodeficiency virus
10. Previous receipt of choleretic agents (e.g. ursodiol, phenobarbital, cholecystikinin). This is done in order to avoid the use of an agent which may reduce cholestasis and the development of PNAC.
11. Current administration of phenobarbital or other barbiturates
12. No infant with a congenital or acquired anomaly which will require major cardiovascular surgery
13. Major congenital or chromosomal anomaly

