each of these four time points is 1. The correlation of any two adjacent measures on the same individual is 0.5. This correlation drops to 0.354 between baseline and 8 weeks and to 0.25 between baseline and 12 weeks.

Using the above assumptions, a sample size of 15 subjects per group using a repeated measures ANOVA will have 85% power to detect the change in slopes as being significant at the 0.05 level, 79% power to detect a difference in means overall between groups and 88% power to detect the general change in means over time across the two groups. When the sample size is increased to 20 subjects per group, the above power numbers increase to 95%, 90% and 96%, respectively. If 30 subjects are recruited per group this design will allow for a 33% attrition rate by twelve weeks as we expect that not all patients will require PN for the full 12 weeks of the initial study period. Thus, we will recruit a minimum of 30 subjects per group to ensure adequate power to detect our primary outcome measure.

Of the secondary outcomes, sample size was also calculated for the incidence of cholestasis. Assuming an incidence of 50% in the standard group and an incidence of 10% in the minimization group, with $\alpha = 0.05$ and power of 80%, a sample size of 23 is required for each group. Regarding the other secondary outcomes, our sample size is large enough to allow for establishing trends which may then highlight avenues for future research.

Planned Statistical Analysis

All data analysis will be directed and performed by a statistician through the Center for Statistical Consultation and Research at the University of Michigan (<http://cscar.research.umich.edu/about/>). Data will be analyzed using SAS software release 9.3 for Windows (Copyright, SAS Institute Inc., SAS and all other SAS Institute Inc. product of service names are registered trademarks or trademarks of SAS Institute Inc., Cary, NC, USA). All study subjects will be included in the statistical analysis in an intent-to-treat manner.

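### The primary bilirubin-slope model names no baseline covariate, although the plan identifies low birth weight and prematurity as PNAC risk factors and adjusts other outcomes for birth weight, gestational age or diagnosis

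*Combined protocol and SAP*

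**What the plan says.** **Primary model.** Planned Statistical Analysis, Primary Outcome Measure, specifies a linear mixed model with a random intercept and a random slope for each infant. It names no baseline covariate. The general paragraph of that section adds septicemia, which arises after randomisation.

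**Prognostic factors.** The Background states: "Well-characterized risk factors for the development of PNAC include prematurity, low birth weight". Data Collection records birth weight, gestational age and inclusion diagnosis.

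**Other models.** The growth models (Secondary Outcome Measures, item 4) use gestational age and birth weight. The neurodevelopment models (item 5) are described as "controlling for important demographic variables, such as gestational age, diagnosis, bilirubin (total and direct"). The PNAC models (items 1 and 3) name sepsis, average IVFE dose and enteral percentage, all measured after randomisation. Both of those lists are introduced as examples.

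**Population.** Inclusion Criteria: "Study subjects will be neonates and infants who are ≥ 28 weeks corrected gestational age at the time of enrollment", with any of six diagnoses, one of which is "Intestinal atresia with >50% bowel loss as defined by bowel length nomogram". Exclusion Criteria remove "Birthweight <1kg". Randomization is within center, stratified by gestational age below or from 32 weeks.

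**Feeding.** Potential Confounding Variables says of standardised feeding advancement: "This will be possible because of the relatively homogeneous nature of the subjects enrolled and their similar expected ability to tolerate enteral feeds". The next sentence adds: "Statistical analyses will account for variations in enteral intake".

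**The concern.** The plan treats birth weight, gestational age and diagnosis as important for secondary outcomes, but does not name them for the bilirubin outcome to which the Background links two of them. Whatever these variables explain of the between-infant variation in slope stays in the error term of the primary comparison. The gestational-age stratum is built into the randomisation and then not named in the primary analysis.

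The trial is small: 60 infants, with power argued on 20 per arm because "this design will allow for a 33% attrition rate by twelve weeks as we expect that not all patients will require PN" for the whole period. Baseline values fixed before assignment can be adjusted for without introducing bias. At stake is precision, together with leaving the covariate choice open until the data are seen.

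**Working it through.** **Inputs (Sample Size Determination).** Means at weeks 0, 4, 8 and 12 are 0.55, 1, 1.5, 2 (standard) and 0.45, 0.5, 0.45, 0.5 (IFER). The SD is 1. Correlations are 0.5 adjacent, 0.354 two visits apart (stated for baseline to week 8, assumed also for weeks 4 to 12) and 0.25 three apart. Alpha is 0.05, taken as two-sided.

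**The plan's own figures.** Repeated-measures ANOVA with the Geisser-Greenhouse correction, by the analytic approximation, gives 84.7% and 94.4% power for slopes at 15 and 20 per arm. The plan states 85% and 95%. Attrition: 20/(1 − 0.33) ≈ 30 per arm. The plan's basis is reproduced.

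**Slope contrast.** Least-squares weights are (−6, −2, 2, 6)/80.
- Slopes: 0.12125 and 0.0025; difference 0.11875 mg/dL/week.
- Variance of one infant's slope: 0.0125 + 2 × (0.5 × 0.003125 − 0.354 × 0.00375 − 0.25 × 0.005625) = 0.01016; SD 0.101.
- SE of the difference at 20 per arm: √(2 × 0.01016/20) = 0.0319.
- Noncentrality: 0.11875/0.0319 = 3.73 on 38 df; power 95.3%.

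**Adding baseline terms.** With k covariate-by-time terms that explain a share R² of slope variance, and N = 40, the variance is multiplied by (1 − R²)(N − 3)/(N − k − 3), on 38 − k df. Break-even for the variance is R² = k/37. The documents give no R², so the range is an assumption.

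| Terms by time | k | Break-even R² | Power, R² = 0 | R² = 0.10 | R² = 0.30 |
|---|---|---|---|---|---|
| Birth weight | 1 | 2.7% | 94.7% | 96.5% | 99.0% |
| Birth weight, stratum | 2 | 5.4% | 94.1% | 96.0% | 98.8% |
| Birth weight, three diagnosis groups | 3 | 8.1% | 93.5% | 95.5% | 98.6% |
| Birth weight, stratum, three diagnosis groups | 4 | 10.8% | 92.8% | 95.0% | 98.3% |
| Birth weight, all six diagnoses | 6 | 16.2% | 91.1% | 93.6% | 97.7% |

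**Main effects only.** A generalised least-squares check with complete data gives an SE for treatment by time of 0.0318 both without covariates and with covariate main effects. Only the interaction with time can sharpen the slope comparison.

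**PNAC models.** On the plan's 50% and 10%, expected events are 30 × 0.5 + 30 × 0.1 = 18. On the 43% and 22% of the retrospective surgical cohort in the Background, they are 12.9 + 6.6 = 19.5. Treatment, three named covariates and three new baseline terms make 7 parameters, or 18/7 ≈ 2.6 events each.

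**The case against.** A reader might infer that the plan drops these covariates because it assumes homogeneous infants. The documents do not support that. The homogeneity sentence explains why feeding can be standardised, and the sentence after it promises to account for variation in intake. The claim is also qualified: several entry criteria select more severe disease, infants under 1 kg are excluded, and the population was chosen for its limited feeding tolerance. The 33% allowance does not show that tolerance differs by diagnosis. This part of the objection stands, and there is no case for deleting the sentence or for replacing the planned enteral adjustment with description.

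A reader might also infer bias, or precision thrown away for nothing. Neither follows. Under randomisation the unadjusted slope comparison is unbiased, and its standard error already covers chance imbalance; stratifying by gestational age should partly balance birth weight as well. Adjustment has a price that is recovered only if R² exceeds the break-even value, and the plan already has about 95% power on its own assumptions.

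Finally, the PNAC lists are open, so it is accurate to say that they do not name birth weight or diagnosis, but not that they exclude them. With about 18 events, adding terms could do harm, and in Cox or Poisson models adjustment does not generally shrink the standard error of the treatment effect.

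What the objection does not answer is the inconsistency: no baseline covariate, not even the stratification factor, is named for the primary outcome, while other models use these same variables.

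**Conclusion.** The point holds for the primary model as a matter of precision and prespecification, not validity. At 20 per arm and the plan's difference, birth weight by time costs 0.6 points of power if it explains nothing (95.3% to 94.7%) and gains 1.2 points at R² 0.10. Birth weight with three diagnosis groups costs about 2 points at worst and gains about 3 at R² 0.30, with break-even near 8%. Using all six diagnoses needs about 16% and is hard to justify. For the PNAC models no gain from extra terms is established.

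These figures assume two-sided alpha, complete data on 20 infants per arm, covariates independent of arm, and the plan's SD and correlations. The direction of the net effect depends on an R² that the documents do not supply.

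**What to change.** Before unblinding, prespecify in the primary mixed model:
- birth weight and birth weight by time;
- the gestational-age stratum used in randomisation (one further slope term if it also interacts with time, as in the table);
- optionally, inclusion diagnosis in three fixed groups, by time, for example surgical NEC; gastroschisis or omphalocele; and meconium ileus/peritonitis, volvulus or atresia.

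State that the list is closed. In the PNAC models, close the open-ended lists as well; keep any baseline terms few, and do not simply add them to the three covariates already named.

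The cost is SAP wording, since the data are already collected, plus a loss of up to about 2 points of power with birth weight and three diagnosis groups if these variables explain nothing (about 2.5, from 95.3% to 92.8%, if the stratum by time is added). The diagnosis grouping must be fixed before unblinding.
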